3.8.2 Sample Size and Power

The primary endpoint of this study component is proportion of cases (newly diagnosed and previously diagnosed but not in care) with a CD4 cell count and/or VL measurement within three months of the diagnostic WB.

Randomization is by testing site, with balance achieved for baseline volume of testing and baseline linkage-to-care rates. Accrual of participants into the Linkage-to-Care

component of the study will occur over the first 24 months of the study, when eligible persons receive the FI coupon at an HIV test site randomized to the FI arm of the study. There will be no follow-up for this component of the study, other than the two visits in care (or a combined lab/provider intake visit).

In 2007, in the 20 testing sites with the highest volume in the Bronx, NY, 611 newly diagnosed HIV-infected people were identified. Of those, 77% were liked to care within three months, with linkage at different testing sites ranging from 30% to 100%. The mean number of newly diagnosed cases per provider in 2008 was 31, and ranged from five to 93. The intra-class correlation (ICC) of proportion linked to care in the Bronx was 0.27.

In 2008, in the 20 testing sites in Washington, D.C, the jurisdiction with the highest volume of people testing HIV-positive, 783 newly infected cases were identified. Of these, 67% were linked to care, ranging across different testing sites from 5% to 100%. The mean number of newly diagnosed cases per provider in 2008 was 40, and ranged from eight to 143. The ICC of proportion linked was 0.31.

These estimates do not include the population of those re-linking to care. It is anticipated that linkage success in SOC for this population will be lower because of the history of loss to care. We could reasonably expect that: 1) the number of people eligible for linkage-to-care will be higher because of longer study duration and addition of re-linked to care cases; 2) the proportion linked to care will be lower because of the re-linked to care cases; and, therefore, 3) the ICC will be smaller. It is assumed that the number of cases to be linked to care during the 24-month study duration will be similar to these past case loads on an annual basis. We will randomize 20 testing sites in each intervention city, and we expect to identify between 1200 and 2400 individuals for linkage-to-care, a mean of 60-120 people per testing site.

Table 2 below gives the mean number of linkage cases needed per testing site to detect an increase in linkage-to-care given 20 sites per arm (*i.e.* 40 in all). With a mean ranging from 80 to 100 linkages per site during the 24 months of the study, we would have 80% power, even with a high ICC, to detect a 13% change in proportion linked to care. If higher numbers are eligible for intervention due to linkage-to-care (*e.g.* 140), we would attain 90% power to detect this magnitude of difference. Note that the ICC coefficient estimated from the linkage-to-care of newly detected cases is high in large part because of sites with a small number of newly detected cases and 100% success in linking to care. It is probable that the ICC observed in the trial will be lower.

This sample size calculation for clustered designs uses the approach described by Thomson, Hayes and Cousens (Hayes and Bennett 1999; Thomson, Hayes et al. 2009).

 Table 2.
 Mean number at each site required to achieve sufficient power to detect differences in proportion of newly detected or reconnected to care within three months of testing. Number of clusters fixed at 20 per arm

Mean percentage linked to care at a site		Standard deviation can	-	Intra-class	Mean number of potential cases for linkage-to-care per testing site	
Standard of care	Intervention	Standard of care	Intervention	correlation	80% power	90% power
67%	80%	17%	12%	0.127	37	49
67%	80%	20%	15%	0.183	54	72
67%	80%	26%	19%	0.309	102	137
67%	75%	17%	14%	0.127	105	140
67%	75%	20%	17%	0.183	152	203
67%	75%	26%	22%	0.309	287	384

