Patient and Provider Surveys: The same computer system used for the Prevention for Positives intervention will be used to administer a survey to patients enrolled in that study component. The survey will assess their knowledge and attitudes towards ART use for treatment and prevention, ART adherence and FIs. Providers from these sites will be invited to complete a Web-based survey regarding their knowledge, attitudes and practices concerning ART for treatment and prevention as well as use of FIs. Both surveys will also collect some key sociodemographic data on surveyed populations to allow more in depth characterization of these populations.

Study Size: Each of the five study components has a target sample size.

- The universal offer of HIV testing will be made in EDs and during hospital admission at ~seven facilities in the Bronx, NY and ~seven in Washington, D.C. Additional focused messages promoting testing will be targeted to the entire population of each intervention community: the Bronx (population 1.4 million) and Washington, D.C. (population 600,000).
- The Linkage-to-Care component includes 40 HIV test sites (20 in each intervention community) and 40 HIV care sites (20 in each intervention community). We project that, by the end of the study, approximately 3000 new individuals in the two intervention communities will have tested positive for HIV.
- The Viral Suppression component includes the 40 HIV care sites (20 in each intervention community). Throughout the study duration, approximately 30,000 HIV-positive individuals will be in care, with an estimated 75% (22,500) eligible for ART in the two intervention communities.
- The Prevention for Positives component will be conducted at a total of twelve sites (six in each intervention community) with up to a total of 1320 patients participating.
- The patients at the twelve sites participating in the Prevention for Positives component will be surveyed. Providers at all participating HIV care sites will be invited to complete the provider survey.

HPTN 065 TLC-Plus: A Study to Evaluate the Feasibility of an Enhanced Test, Link to Care, Plus Treat Approach for HIV Prevention in the United States

OVERVIEW OF STUDY DESIGN AND RANDOMIZATION SCHEME

Summary of Study Components

Study Component	Design	Outcomes
Expanded HIV Testing	Descriptive, ecologic study	Feasibility
Linkage-to-Care	Two-arm, site-randomized, prospective, effectiveness study	Feasibility and effectiveness

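### Table 2 overstates power for linkage-to-care: with 20 test sites per arm and ICC 0.309, power for 67% vs 80% is about 41%, not 80%, whatever the number of cases per site

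*Protocol*

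**What the plan says.** Protocol section 3.8.2 sizes the primary linkage-to-care comparison, the proportion linked within three months. On method it states: "This sample size calculation for clustered designs uses the approach described by Thomson, Hayes and Cousens". Table 2 is headed "Number of clusters fixed at 20 per arm". Its high-clustering row reads "67% 80% 26% 19% 0.309 102 137": control and intervention percentages, between-site SDs, ICC, then cases per site for 80% and 90% power.

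From the table the text concludes that, at an average of 80 to 100 cases per site over the 24 months, "we would have 80% power, even with a high ICC, to detect a 13% change in proportion linked to care". It adds that about 140 per site would give 90%.

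The same section reports ICCs of 0.27 (Bronx) and 0.31 (Washington, D.C.) from past data. It expects a lower ICC in the trial, partly because people re-linking to care will be added. On volume it says: "we expect to identify between 1200 and 2400 individuals for linkage-to-care, a mean of 60-120 people per testing site".

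**The concern.** When the number of clusters is fixed, extra cases per cluster reduce only the within-site part of the variance. The between-site part stays and puts a ceiling on power. Table 2 instead shows power rising from 80% to 90% when cases per site go from 102 to 137 at an ICC of 0.309, where the between-site part dominates. That pattern suggests that the case columns do not follow from the SD and ICC columns.

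Two things are at stake. The component is presented as adequately powered under pessimistic clustering. And the table tells the team that low power can be cured by more cases per site, when only more sites or less between-site variance would help.

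**Working it through.** **Inputs.** From section 3.8.2 and Table 2: c = 20 sites per arm; p0 = 0.67; p1 = 0.80 or 0.75; SDs, ICCs and cases per site m as listed. Alpha is not given for this component. Two-sided 5% is assumed, as stated for Prevention for Positives in section 5.9.2. Control-arm SDs match the listed ICCs (0.26²/0.2211 = 0.306). Intervention-arm SDs imply lower ones (0.19²/0.16 = 0.226), so both routes below are shown.

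**Trying to reproduce the plan's figure.** The individually randomized n per arm for 67% vs 80% is (1.96 + 0.84)² × (0.2211 + 0.16)/0.13² ≈ 177 for 80% power (180 with pooled variance) and 237 (240) for 90%. The past caseload is (611 + 783)/40 = 34.85 per site per year. Holding the design effect at that size gives 1 + 33.85 × 0.309 = 11.46. Then:

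- 80% power: 177 × 11.46/20 = 101 (103 pooled); table 102.
- 90% power: 237 × 11.46/20 = 136 (138 pooled); table 137.
- 67% vs 75% (n = 501 and 671): 287 and 384; table 287 and 384.

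So the ICC 0.309 rows reproduce with a frozen design effect. The lower-ICC rows reproduce in the same way only with frozen sizes of about 26 and 29. The protocol does not describe this step; it is inferred from the match.

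**Why this fails.** At m = 102 the design effect is 1 + 101 × 0.309 = 32.2, not 11.5. Letting it grow with m gives m = n(1 − ICC)/(20 − n × ICC), which has a solution only if n × ICC < 20. For 67% vs 80%, 177 × 0.309 = 54.7, and even 177 × 0.127 = 22.5. For 67% vs 75%, 501 × 0.127 = 63.6. No row can reach 80% power with 20 sites per arm.

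**Power by the cited method.** c = 1 + (z_α/2 + z_β)² V/(p1 − p0)², with V = p0(1 − p0)/m + p1(1 − p1)/m + s0² + s1². At c = 20, power = Φ(√(19(p1 − p0)²/V) − 1.96).

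High-ICC row, m = 102: V = 0.2211/102 + 0.16/102 + 0.0676 + 0.0361 = 0.1074. √(19 × 0.0169/0.1074) − 1.96 = −0.23, so power is 41%.

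| Comparison | ICC | Table m (80% / 90%) | Power at those m | Ceiling, m → ∞ | Sites per arm for 80% at the 80%-column m |
|---|---|---|---|---|---|
| 67 vs 80% | 0.127 | 37 / 49 | 69% / 71% | 78% | 25.9 |
| 67 vs 80% | 0.183 | 54 / 72 | 57% / 59% | 62% | 33.3 |
| 67 vs 80% | 0.309 | 102 / 137 | 41% / 41% | 42% | 50.9 |
| 67 vs 75% | 0.127 | 105 / 140 | 33% / 34% | 35% | 65.3 |
| 67 vs 75% | 0.183 | 152 / 203 | 26% / 26% | 26% | 88.8 |
| 67 vs 75% | 0.309 | 287 / 384 | 17% / 17% | 17% | 145.0 |

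At the case numbers in the text, ICC 0.309 gives 40.5% (m = 80), 40.8% (m = 100) and 41.2% (m = 140). ICC 0.127 gives 73% and 74% at m = 80 and 100.

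**Cross-checks, ICC 0.309.** With a common ICC in both arms, the design-effect formula gives 38% at m = 102. Beta-binomial simulation with a t-test on site proportions gives 37% (common ICC) to 41% (Table 2's SDs).

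**Detectable gain at 80% power, m = 100.**

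- ICC 0.309, common to both arms, 21 points (p1 = 0.88): V = 0.0033 + 0.0683 + 0.0326 = 0.1042; √(19 × 0.0441/0.1042) − 1.96 = 0.88; power 81%.
- ICC 0.27, 20 points (p1 = 0.87): V = 0.0033 + 0.0597 + 0.0305 = 0.0936; power 81%.
- ICC 0.127 with Table 2's SDs, 14 points (p1 = 0.81): V = 0.0037 + 0.0289 + 0.0144 = 0.0470; power 80%.

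**The case against.** The best defence has four parts.

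- **Alpha.** It is unstated, so one-sided 5% is possible. That gives 53% in the high-ICC row at m = 102. At ICC 0.127 it gives 79% at m = 37, close to the table's 80%, but only 81% at m = 49 against the table's 90%. It rescues neither the disputed sentence nor the table.
- **A lower ICC is expected.** The protocol gives reasons for this, but the sentence claims 80% at a high ICC, and 0.27 and 0.31 are its own baseline values. At two-sided 5%, 80% power with 80 to 100 cases per site needs an ICC of about 0.10, below every row of the table.
- **Balancing.** Sites are balanced on volume and baseline linkage, which may reduce the effective between-site variance. This has some force at low ICC: at 0.127, removing about 14% to 17% of that variance would reach 80% at 80 to 100 cases per site. At 0.309 about 65% would have to go. Table 2 takes no such credit, and the GEE analysis in section 3.8.4.1 names no such adjustment.
- **Purpose.** The protocol calls the study formative, and a confidence interval would still show which effects a null result excludes. This limits the harm but does not make the stated power right.

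A reader might also infer that the caseload figures are wrong. The documents do not support that:

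- The 80 to 100 cases lie inside the plan's own 60 to 120 per site.
- Doubling the past annual load gives 2 × 34.85 = 70 per site, and the Schema projects that "approximately 3000 new individuals in the two intervention communities will have tested positive for HIV" (3,000/40 = 75 per site). Both count new diagnoses only, while the 80 to 100 include re-linkage cases whose number is not given. No excess can be shown.
- Reading 60 to 120 as an error for 30 to 60 assumes that 1200 to 2400 is the total for both cities. Divided by 20 sites per city it gives exactly 60 to 120, and the doubled annual loads (1,222 and 1,566) fit that range. The wording is ambiguous, not wrong.

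**Conclusion.** The power statement and Table 2 are wrong as written. At the high ICC, power for 67% vs 80% is about 41%, roughly half the stated figure, and moving to 140 cases per site adds less than one point instead of taking power to 90%. All six rows fall short of their stated power.

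The result rests on 20 sites per arm, Table 2's own proportions and SDs, the cited cluster formula, an assumed two-sided 5% level, and no credit for balancing. The ICC 0.309 figures hold under every variant tried (37% to 53%). The ICC 0.127 figures depend more on the assumptions: one-sided testing, or a modest credit for balancing, would bring that row to about 80% or a little above at 80 to 100 cases per site.

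The caseload figures do not bear on this, because at ICC 0.309 power barely changes with cases per site (40% at 61, 41% at 102).

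**What to change.** - Recompute Table 2 for 20 sites per arm, with alpha and sidedness stated and power shown at realistic case numbers.
- Replace the 80% sentence with the recomputed values. At two-sided 5% and 80 to 100 cases per site, power for 67% vs 80% is about 40% at ICC 0.309 and about 73% to 74% at ICC 0.127. The detectable gain at 80% power is about 20 to 21 points at ICC 0.27 to 0.31 and about 14 points at ICC 0.127.
- Delete the claim that 140 cases per site gives 90% power.
- If credit is taken for balancing or adjusting on baseline linkage, state the assumed reduction in between-site variance as an assumption.
- As a wording note only, say whether 1200 to 2400 is per city or in total.

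The cost is one table and a few sentences. No sites or procedures need be added; the stated power becomes less favourable.

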3.8.3 Randomization Scheme

In the Linkage-to-Care study component, HIV testing sites will be randomized to use FIs or the SOC.

HIV test sites will be assigned to one of the following two arms:

- An arm offering FIs: Test sites assigned to this arm will provide coupons to all individuals testing HIV-positive, who are not already linked to HIV care. The coupons can be redeemed for the FI at a participating HIV care site.
- An arm continuing with SOC: Each person who tests HIV-positive, and is not currently in care, will be directed to HIV care sites using the site's SOC procedures.

The site randomization will be balanced by the following two baseline characteristics:

- The number of HIV-positive individuals identified in the previous year
- The rate of linkage-to-care within three months of HIV diagnosis over the course of the calendar year prior to study initiation

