2.4 Study Sites for Expanded HIV Testing

2.4.1 Hospital/ED Study Sites in the Bronx, NY

Efforts to expand HIV testing will be undertaken at approximately seven Bronx hospitals with at least a Level I trauma center/ED and with daily hospital admissions. Overall, total ED visits at these hospitals in 2006 ranged from 49,635 to 134,969 per hospital.

2.4.2 Hospital/ED Study Sites in Washington, D.C.

Efforts to expand HIV testing will be undertaken at approximately seven Washington, D.C. hospitals. Routine HIV testing through the ED at George Washington University Hospital and throughout Howard University Hospital, begun in 2006, accounted for nearly 25% of all publicly supported tests in Washington, D.C. and 20% of reported positives in the HIV testing data in 2008.

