The study will also provide EDs with a downloadable computer widget application on routine HIV testing that can be placed on the desktops of all ED computer terminals (either an updated version of the tool created by St. Vincent's Medical Center, with funding from the New York State AIDS Institute, or a similar tool). This widget will not only provide the full CDC Guidelines for routine HIV screening, but will include brief checklists that walk providers through the process of obtaining written consent (currently still required in NY), conducting an HIV test, providing results and handling a positive HIV diagnosis.

In working with the complex logistics in EDs, the study team will also operate within existing hospital admission processes as much as possible.

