2.6.3.1 Emergency Departments

Washington, D.C. EDs have been focal points for the implementation of routine HIV screening because many Washington, D.C. residents only access healthcare through the city's EDs. HIV testing in EDs can be integrated as a routine, opt-out procedure because Washington, D.C. does not require a separate written consent form for HIV testing. Patients are provided with written or verbal information about HIV testing, advised that a test is recommended, and (depending on available staff) a point-of-care rapid test is performed, unless the patient declines. In addition to the two institutions currently conducting routine testing in EDs, the Washington, D.C. DOH has begun to engage six additional EDs to undertake routine, opt-out HIV testing. HAHSTA recently completed review of a Request for Applications (RFA) to support expansion of routine HIV screening in EDs and hospital centers by providing support for a part-time coordinator at each hospital to promote implementation of routine testing. A coordinator at each facility will work with hospital leadership and department heads (CEOs and medical, lab and data staff) to develop plans for routine HIV screening in the ED and in other departments in the hospital system. In Washington, D.C., health insurers are required to reimburse for a voluntary HIV test performed during an insured's visit, regardless of the reason for that ED visit. Study funds will be used to support the cost of tests for patients who are uninsured. In addition, the study will support a part-time coordinator at each institution, working with management and ED and laboratory staff toward implementation of routine screening. The Washington, D.C. DOH will provide TA, including staff training, to all partnering hospitals.

Washington, D.C. has developed a provider toolkit for routine, opt-out HIV testing that includes an introductory brochure, pocket card, result cards and opt-out card. These tools define routine, opt-out HIV testing and provide checklists for the screening process, from test introduction to the provision of follow-up appointments for HIV-positive individuals. These materials will be available for wide distribution to the staff of partnering EDs participating in routine, opt-out HIV testing and to clinical providers throughout Washington, D.C.

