3.4 Study Sites for Linkage-to-Care

Twenty HIV test sites will be selected from Washington, D.C. and 20 HIV test sites will be selected from the Bronx to participate in the Linkage-to-Care component of this study.

HIV test sites will be selected based on two primary criteria: 1) site agreement to participate in this component of the study, and 2) sites with the highest volume of HIV-positive individuals identified in the previous year. Additional site selection criteria may be considered if a total of 40 HIV test sites cannot be chosen based on the primary criteria.

In each community, these 20 sites will be randomized such that 10 will use the FI intervention, described in Section 3.5, to link HIV-patients to care and 10 will use the SOC only.

The site randomization will be balanced by the following two baseline characteristics:

- The number of HIV-positive individuals identified in the previous year
- The rate of linkage-to-care within three months of HIV diagnosis over the course of the calendar year prior to study initiation

In addition, 20 care sites will be selected in Washington, D.C. and 20 care sites will be selected in the Bronx, NY. These care sites will redeem the coupons provided to patients by the test sites selected for the FI arm.

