3.6.3 Monitoring HIV Test Sites

It is possible that members of the intervention communities will learn of the FI to strengthen linkage-to-care and seek out HIV test sites offering these incentives. In all likelihood, the majority of individuals who seek testing will not know their HIV status yet and, thus, will be unaware that incentives are being offered for linkage-to-care. In addition, many of the HIV test sites in the study (~seven out of the 20 participating HIV test sites in each city) will be hospitals in which HIV testing will take place in emergency departments and inpatient units. Individuals seen in these settings are usually not there for the purpose of obtaining an HIV test. Thus, it is unlikely that these individuals will seek medical services based on the availability of FIs for linkage to HIV care.

However, it is possible that some individuals, who are aware of their HIV infection, may "recycle" through the HIV test sites due to the availability of FIs. There are some natural barriers to this phenomenon, as it is likely that the staff at these HIV test sites will recognize individuals who are testing with undue frequency. In these cases, staff may withhold the FI coupons from those who have already received them for a prior HIV-positive test. Another natural barrier is that individuals are known at HIV care sites, so individuals will be unable to re-link repeatedly to the same HIV care site. In addition, the FI intervention is designed such that multiple activities (lab-work and provider

interaction, both of which take time and effort) are required for the full redemption, which may discourage some from repeated linkage.

It should also be noted that based on the HIV prevalence in the intervention cities, relatively few people test positive out of all of those who test. Thus, the number of people who could "recycle" through the HIV test sites is relatively small compared to the total testing done in these venues.

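### Linkage-to-Care randomisation is not balanced on hospital status, although about 7 of 20 test sites per city are hospitals that very likely also receive the study's expanded-testing support; a third balancing factor would cheaply limit chance imbalance

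*Protocol*

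**What the plan says.** Sections 3.4 and 3.8.3 randomise 20 HIV test sites in each city, 10 to financial incentives (FI) and 10 to standard of care (SOC). Both sections fix the same pair of balancing factors: "The site randomization will be balanced by the following two baseline characteristics". One is the number of HIV-positive individuals found in the previous year. The other is "The rate of linkage-to-care within three months of HIV diagnosis over the course of the calendar year prior to study initiation".

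Section 3.6.3 adds that about "seven out of the 20 participating HIV test sites in each city) will be hospitals in which HIV testing will take place". The settings it names are the emergency department and the inpatient wards. In the Expanded HIV Testing component, section 2.4.1 reads "Efforts to expand HIV testing will be undertaken at approximately seven Bronx hospitals" and section 2.4.2 reads "Efforts to expand HIV testing will be undertaken at approximately seven Washington, D.C. hospitals". The protocol does not say outright that the two sets coincide, but the counts and settings match.

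Hospitals in that component receive the following from the study:

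- **Bronx (2.6.2):** a team that works on universal offer of testing, quarterly feedback, free kits for uninsured patients, help with standing orders, and a desktop tool that covers "conducting an HIV test, providing results and handling a positive HIV diagnosis".
- **D.C. (2.6.3):** a part-time coordinator, staffing funds and work on standing orders. Emergency departments also get the health department's toolkit, with checklists running "from test introduction to the provision of follow-up appointments for HIV-positive individuals".

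Section 2.8.2 says that enhanced access at hospitals lasts the full 36 months, so it overlaps the 21 months of coupon distribution in section 3.7. The primary analysis in 3.8.4.1 is a GEE odds ratio with within-site correlation. Type of testing venue appears only in the descriptive feasibility analysis in 3.8.4.2.

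**The concern.** The linkage trial is meant to isolate the coupon. About a third of its sites very likely receive a second HPTN 065 intervention at the same time, and nothing in the allocation spreads those sites evenly between arms.

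Both balancing factors describe the year before the study. They deal with differences that already exist, including the venue differences in time to care that section 1.1.3 reports. They cannot deal with what changes once hospital support begins. Sections 2.6.2.2 and 2.6.3.2 say that no NYC hospital had implemented universal offer at admission and that no D.C. hospital screened routinely at admission. Hospital volume and case mix can therefore be expected to move after baseline, and linkage may move with them.

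If hospitals fall unevenly, part of the observed difference between arms would reflect where the hospitals landed.

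**Working it through.** **Inputs**

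- 20 sites per city, 10 per arm (3.4); about 7 hospitals among the 20 (3.6.3).
- Design differences in Table 2: 80 − 67 = 13 points and 75 − 67 = 8 points.
- Between-site SDs in Table 2, as SOC/FI: from 17/12 to 26/19 points for the 13-point difference.
- Assumed change in hospital linkage relative to other sites after support starts: 5, 10 or 15 points. This is not in the protocol.
- Assumed independence of hospital status from the two balancing factors.

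The protocol gives no figure of its own on this point to reproduce.

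**Step 1: split within one city.** The number of hospitals in the FI arm is hypergeometric: P(k) = C(7,k) × C(13,10−k) / C(20,10), with C(20,10) = 184,756.

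- 3-4 or 4-3: 2 × 35 × 1,716 = 120,120, and 120,120 / 184,756 = 65.0%.
- 5-2 or worse: 100% − 65.0% = 35.0%.
- 6-1 or worse: 5.7%.
- 5-2 or worse in at least one of two cities: 1 − 0.650² = 57.7%.

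**Step 2: both cities pooled.** The primary comparison and Table 2 concern 40 sites, so the pooled difference is the one that matters. Convolving the two city distributions (14 hospitals among 40 sites) gives:

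- difference of 4 or more hospitals between arms: 32.7%
- difference of 6 or more: 10.0%

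**Step 3: shift in the contrast.** With sites weighted equally, shift = (difference in number of hospitals / sites per arm) × assumed hospital shift.

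| Imbalance | 5 points | 10 points | 15 points |
|---|---|---|---|
| Pooled difference of 4 (4/20) | 1.0 | 2.0 | 3.0 |
| Pooled difference of 6 (6/20) | 1.5 | 3.0 | 4.5 |
| One city, 5-2 (3/10), that city's contrast only | 1.5 | 3.0 | 4.5 |

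**Step 4: comparison with the noise already assumed.** The between-site SDs alone give a standard error for the arm difference of √((17² + 12²)/20) = 4.7 points up to √((26² + 19²)/20) = 7.2 points. A 10-point hospital shift adds a between-site variance of 0.35 × 0.65 × 10² = 23 points², which is 8% of 17² = 289 and 3% of 26² = 676.

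**Step 5: after balancing on hospital status.** Each city splits 3-4 or 4-3, so the pooled difference is at most 2 hospitals. The shift is at most 2/20 of the assumed value: 0.5, 1.0 or 1.5 points.

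**The case against.** The strongest reply is that this is ordinary chance imbalance between clusters. Hospitals are allocated at random, so the contrast is unbiased in expectation, and the cluster analysis already allows for sites that differ. Step 4 shows that a shift of 1 to 3 points is modest against a standard error of about 5 to 7 points. This stands, and it limits the point to precision.

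Three stronger readings are tempting, and the protocol supports none of them.

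- **A reader might infer that the hospital effect cannot be separated from the coupon effect.** It can. Hospital status is a known site attribute. The chance that all seven hospitals in a city fall in one arm is about 0.3%, so hospital and non-hospital sites can almost always be compared within both arms.
- **A reader might infer that only hospitals get help with linkage.** The D.C. toolkit is the city's own and is meant for clinical providers across the city (2.6.3.1). D.C. navigators are citywide (1.1.3.3). Training on linking patients covers all test-site staff (3.6.1). The coordinators, staffing and standing orders aim at testing, and no section says that they change linkage.
- **A reader might set the one-city shift against Table 2.** Table 2 assumes 20 sites per arm, so the pooled shift is the right comparison.

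Two further limits also stand. Hospital testing was already partly under way (2.4.2, 2.6.2.1). If hospitals are the larger sites, balancing on the number of positives balances them in part. The probabilities above are then approximate upper values.

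The objection does not show that prior-year factors capture support that starts afterwards, or that leaving the factor out gains anything.

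**Conclusion.** The point holds as a cheap improvement. The protocol itself fixes the balancing factors, and they leave out a site attribute that is known in advance and tied to another arm of the same study. The consequence is avoidable chance imbalance, not bias. There is about a one-in-three chance of a pooled difference of four or more hospitals, worth 1 to 3 points on the overall contrast against design differences of 8 and 13.

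This rests on four assumptions: that the hospitals in the two components are the same, that there are seven per city, that hospital status is independent of the two existing factors, and that hospital linkage shifts by 5 to 15 points. The last has no support in figures from the protocol. If the support leaves linkage and case mix unchanged, the cost is nil.

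That section 3.8.4.1 names no site-type term is not a fault in itself, because model covariates may be left to the statistical analysis plan. The allocation is different: it cannot be rebalanced after randomisation.

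**What to change.** In sections 3.4 and 3.8.3, add a third balancing factor within each city: hospital site receiving expanded-testing support (yes/no). With seven hospitals, this forces a 3-4 or 4-3 split. Carry the same indicator as a site-level term in the primary linkage model, either in 3.8.4.1 or in the statistical analysis plan. It would also help to state in 3.6.3 that the hospital test sites are those of the Expanded HIV Testing component, if that is so.

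The cost is one more constraint in the allocation and one covariate. The constraint is slightly tighter with 20 sites per city, but before the two existing factors are applied about 65% of the 184,756 possible allocations already satisfy it. It must be set before sites are randomised.
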